**CONFIDENTIAL**

205665

Element	Reporting Detail
	

○ If the partial date is a stop date, a '28/29/30/31' will be used for the day (dependent on the month and year) and 'Dec' will be used for the month.

● The recorded partial date will be displayed in listings.

CONFIDENTIAL

205665

## 14.8. Appendix 8: Values of Potential Clinical Importance

### 14.8.1. Laboratory Values

Haematology				
Laboratory Parameter	Units	Category	Clinical Concern Range	
			Low Flag (< x)	High Flag (>x)
Hemoglobin	G/DL		<8.5 G/DL	>11 G/DL
Platelet Count	GI/L		< 80 GI/L	> 500 GI/L
Neutrophils	GI/L		< 0.5x LLRR	
Lymphocytes	GI/L		< 0.5x LLRR	

Clinical Chemistry				
Laboratory Parameter	Units	Category	Clinical Concern Range	
			Low Flag (< x)	High Flag (>x)
Potassium	mmol/L		> 0.5 mmol/L below LLRR	> 1.0 mmol/L above ULRR
Albumin	g/dL		< 3.0 g/dL	> 5.5 g/dL
AST (SGOT)	IU/L			>= 3x ULRR
ALT (SGPT)	IU/L			>= 3x ULRR
Calcium (Albumin adjusted)	mg/dL		< 7.48 mg/dL	> 10.24 mg/dL
Phosphate	mg/dL		< 2.50 mg/dL	> 5.47 mg/dL
Total bilirubin	μmol/L			>= 2x ULRR
Serum ferritin	ng/mL		< 100 ng/mL	> 800 ng/mL
TSAT	%		<15%	> 40%
Sodium	mmol/L		< 130 mmol/L	> 150 mmol/L
Glucose	mmol/L		<3.9 mmol/L	>22 mmol/L

### 14.8.2. Vital Signs

Vital Sign Parameter (Absolute)	Units	Clinical Concern Range	
		Lower	Upper
Systolic Blood Pressure	mmHg	<= 80 mmHg	>= 160 mmHg
Diastolic Blood Pressure	mmHg	<= 50 mmHg	>= 100 mmHg
Pulse Rate	bpm	<= 40 bpm	>= 110 bpm

Notes:

- At visits where BP and HR are assessed more than once, the average of the values will be used to assess PCI criteria.
- For participants who undergo in-clinic dialysis, the post-dialysis BP and HR values will be used to assess PCI criteria, unless otherwise specified.

## **14.9. Appendix 9: Population Pharmacokinetic (PopPK) Analyses**

PopPK is not evaluated for this study. The primary objective is Pharmacodynamic, the average systolic blood pressure (SBP) over 6-hr post-dosing after 8 weeks, this is described in Section [11](#).

#### **14.10. Appendix 10: Pharmacokinetic / Pharmacodynamic Analyses**

PK/PD is not evaluated for this study. The primary objective is Pharmacodynamic, the average systolic blood pressure (SBP) over 6-hr post-dosing after 8 weeks, this is described in Section [11](#).

CONFIDENTIAL

205665

**14.11. Appendix 11: Abbreviations & Trade Marks****14.11.1. Abbreviations**

Abbreviation	Description
ABPM	Ambulatory blood pressure monitoring
AC	Acute challenge
ADaM	Analysis Data Model
AE	Adverse Event
AESI	Adverse event of special interest
AIC	Akaike's Information Criteria
ALP	Alkaline phosphatase
ALT	Alanine aminotransferase
ANCOVA	Analysis of covariance
AST	Aspartate aminotransferase
AUC	Area under curve
AUEC	Area under effect curve
A&R	Analysis and Reporting
BP	Blood pressure
CDISC	Clinical Data Interchange Standards Consortium
CHF	Chronic heart failure
CHR	Reticulocyte hemoglobin content
CI	Confidence Interval
CKD	Chronic kidney disease
CPMS	Clinical Pharmacology Modelling & Simulation
CS	Clinical Statistics
CSR	Clinical Study Report
CTR	Clinical Trial Register
CV b / CV w	Coefficient of Variation (Between) / Coefficient of Variation (Within)
DBF	Database Freeze
DBP	Diastolic blood pressure
DBR	Database Release
DOB	Date of Birth
DP	Decimal Places
DR	Dry run
eCRF	Electronic Case Record Form
EMA	European Medicines Agency
ESA	Erythropoiesis-stimulating agent
FDA	Food and Drug Administration
FDAAA	Food and Drug Administration Clinical Results Disclosure Requirements
GSK	GlaxoSmithKline
HD	Hemodialysis-dependent
HR	Heart rate
IA	Interim Analysis
ICH	International Conference on Harmonization
IDMC	Independent Data Monitoring Committee

**CONFIDENTIAL**

205665

Abbreviation	Description
IDSL	Integrated Data Standards Library
IMMS	International Modules Management System
IP	Investigational Product
ITT	Intent-To-Treat
MAP	Mean arterial blood pressure
MCH	Mean corpuscular hgb
MCHC	Mean corpuscular hgb concentration
MCV	Mean corpuscular volume
MI	Myocardial Infarction
MMRM	Mixed Model Repeated Measures
PCI	Potential Clinical Importance
PD	Pharmacodynamic
PDMP	Protocol Deviation Management Plan
PK	Pharmacokinetic
PP	Per Protocol
PopPK	Population PK
QC	Quality Control
QTcF	Frederica's QT Interval Corrected for Heart Rate
QTcB	Bazett's QT Interval Corrected for Heart Rate
RAP	Reporting & Analysis Plan
RAMOS	Randomization & Medication Ordering System
RC	Reticulocyte count
RDW	Red blood cell distribution width
SAC	Statistical Analysis Complete
SAE	Serious adverse event
SBP	Systolic blood pressure
SDSP	Study Data Standardization Plan
SDTM	Study Data Tabulation Model
SOP	Standard Operation Procedure
TA	Therapeutic Area
TFL	Tables, Figures & Listings
WBC	White blood cell count

**14.11.2. Trademarks**

Trademarks of the GlaxoSmithKline Group of Companies
None

Trademarks not owned by the GlaxoSmithKline Group of Companies
HemoCue
SAS

**CONFIDENTIAL**

205665

**14.12. Appendix 12: List of Data Displays****14.12.1. Data Display Numbering**

The following numbering will be applied for RAP generated displays:

Section	Tables	Figures
Study Population	1.01 to 1.19	-
Safety	2.01 to 2.35	-
Pharmacokinetic	3.01 to 3.2	3.01 to 3.21
Pharmacodynamic and Biomarker	4.01 to 4.42	4.01 to 4.12
Pharmacokinetic / Pharmacodynamic	-	5.01-5.02
Section	Listings	
ICH Listings	1 to 30	
Other Listings	31 to 35	

All tables and figures will start with numbering scheme like “X.01, X.02, etc”.

**14.12.2. Mock Example Shell Referencing**

Non IDSL specifications will be referenced as indicated and if required example mock-up displays provided in [Appendix 13](#): Example Mock Shells for Data Displays.

Section	Figure	Table	Listing
Pharmacodynamic and Biomarker	PDF1	PDT1 - PDT10	PDL1
Pharmacokinetic / Pharmacodynamic	PKPDF1	-	-

**NOTES:**

- Non-Standard displays are indicated in the 'IDSL / Example Shell' or 'Programming Notes' column as '[Non-Standard] + Reference.'

**14.12.3. Deliverables**

Delivery	Description
DR	Dry Run
SAC	Final Statistical Analysis Complete

CONFIDENTIAL

205665

## 14.12.4. Study Population Tables

Study Population Tables					
No.	Population	IDSL / Example Shell	Title	Programming Notes	Deliverable
Subject Disposition					
1.1.	Enrolled	ES1	Summary of Subject Status and Reason for Study Withdrawal	ICH E3, FDAAA, EudraCT No sub reason	DR, SAC
1.2.	ITT	SD1	Summary of Treatment Status and Reasons for Discontinuation of Study Treatment	ICH E3 No sub reason	DR, SAC
1.3.	Screened	PDT10	Summary of Participant Disposition at Each Study Period	ICH E3  Add footnote: Withdrawn subjects may be greater than entered for no treatment due to subject's first follow-up visit occurring after second screen failure.	DR, SAC
1.4.	Screened	ES6	Summary of Screening Status and Reasons for Screen Failure	Journal Requirements	DR, SAC
1.5.	Enrolled	NS1	Summary of Number of Participant by Country and Site ID	EudraCT/Clinical Operations	DR, SAC
Protocol Deviation					
1.6.	ITT	DV1	Summary of Important Protocol Deviations	ICH E3	DR, SAC
1.7.	ITT	IE1	Summary of Inclusion/Exclusion Criteria Deviations	ICH E3	DR, SAC

CONFIDENTIAL

205665

Study Population Tables					
No.	Population	IDSL / Example Shell	Title	Programming Notes	Deliverable
Population Analysed					
1.8.	Screened	SP1	Summary of Study Populations	IDSL, all populations to be used (Screened, enrolled, safety, ITT, PP, PK)	DR, SAC
1.9.	ITT	SP2	Summary of Exclusions from the Safety Population	IDSL	DR, SAC
1.10.	ITT	SP2	Summary of Exclusions from the Per Protocol Population	IDSL	DR, SAC
Demographic and Baseline Characteristics					
1.11.	ITT	DM1	Summary of Demographic Characteristics - ITT	ICH E3, GSK CTR, FDAAA, EudraCT Footnote: Age is imputed from year and month of birth	DR, SAC
1.12.	Safety	DM1	Summary of Demographic Characteristics - Safety	ICH E3, GSK CTR, FDAAA, EudraCT Footnote: Age is imputed from year and month of birth	DR, SAC
1.13.	Enrolled	DM11	Summary of Age Ranges	EudraCT Footnote: Age is imputed from year and month of birth	DR, SAC
1.14.	ITT	DM5	Summary of Race and Racial Combinations	ICH E3, FDA, GSK CTR, FDAAA, EudraCT	DR, SAC
Prior and Concomitant Medications					
1.15.	ITT	MH1	Summary of Medical Conditions	ICH E3	DR, SAC

CONFIDENTIAL

205665

Study Population Tables					
No.	Population	IDSL / Example Shell	Title	Programming Notes	Deliverable
1.16.	ITT	CM1	Summary of Concomitant Medications (Pre-treatment)	ICH E3	DR, SAC
1.17.	ITT	CM1	Summary of Concomitant Medications (On-treatment)	ICH E3	DR, SAC
1.18.	ITT	CM1	Summary of Concomitant Medications (Post-treatment)	ICH E3	DR, SAC
Exposure and Treatment Compliance					
1.19.	Safety	EX1	Summary of Exposure and Compliance to Study Treatment	
ICH E3, add line for average percent compliant for each treatment group. Total column not needed.
 
Add the following footnote if unable to calculate dose hold days: Compliance calculation assumed dose hold days and missed doses to be the same.
 
Add footnote, daprodustat only, rhEPO done at site so no compliance to calculate
	DR, SAC

CONFIDENTIAL

205665

Study Population Tables					
No.	Population	IDSL / Example Shell	Title	Programming Notes	Deliverable
Additional Study Population Tables					
1.20.	PP	DM1	Summary of Demographic Characteristics - PP	ICH E3, GSK CTR, FDAAA, EudraCT Footnote: Age is imputed from year and month of birth  Only produce if PP used in sensitivity analyses	SAC

#### 14.12.5. Safety Tables

Safety: Tables					
No.	Population	IDSL / Example Shell	Title	Programming Notes	Deliverable
Adverse Events (AEs)					
2.1.	Safety	AE1	Summary of All Adverse Events by System Organ Class and Preferred Term	ICH E3, by treatment, then summarized by pre-treatment, post-randomization, treatment emergent, and follow-up.	DR, SAC
2.2.	Safety	AE1	Summary of All Adverse Events by System Organ Class and Preferred Term by Phase	Treatment AEs will be separated by AC1, HGB maintenance, and AC2.	DR, SAC
2.3.	Safety	AE3	Summary of Common ( $\geq 2\%$ ) Adverse Events by Overall Frequency	ICH E3, by preferred term and treatment group, includes treatment emergent AEs	DR, SAC

**CONFIDENTIAL**

205665

Safety: Tables					
No.	Population	IDSL / Example Shell	Title	Programming Notes	Deliverable
2.4.	Safety	AE5A	Summary of Common ( $\geq 2\%$ ) Adverse Events by Maximum Intensity	ICH E3, by treatment, includes treatment emergent AEs	DR, SAC
2.5.	Safety	AE1	Summary of All Drug-Related Adverse Events by System Organ Class and Preferred Term	ICH E3, by treatment, includes treatment emergent AEs	DR, SAC
2.6.	Safety	AE1	Summary of All Serious Drug-Related Adverse Events by System Organ Class and Preferred Term	By treatment, includes treatment emergent AEs	DR, SAC
2.7.	Safety	AE1	Summary of All Non-Serious Drug-Related Adverse Events by System Organ Class and Preferred Term	By treatment, includes treatment emergent AEs	DR, SAC
2.8.	Safety	AE15	Summary of Common ( $\geq 2\%$ ) Non-serious Adverse Events by System Organ Class and Preferred Term (Number of Participant and Occurrences)	FDAAA, EudraCT, by treatment group, includes treatment emergent AEs	DR, SAC
2.9.	Safety	AE5A	Summary of Common ( $\geq 2\%$ ) Drug Related Adverse Events by Maximum Intensity	ICH E3, by treatment group, includes treatment emergent AEs	DR, SAC
2.10.	Safety	AE5A	Summary of All Adverse Events by System Organ Class and Preferred Term and Maximum Intensity	ICH E3, by treatment, then summarized by pre-treatment, post-randomization, treatment emergent, and follow-up.	SAC
2.11.	Safety	AE1	Summary of AEs of Special Interest	By treatment	SAC

## CONFIDENTIAL

205665

Safety: Tables					
No.	Population	IDSL / Example Shell	Title	Programming Notes	Deliverable
Serious and Other Significant Adverse Events					
2.12.	Safety	AE16	Summary of Serious Adverse Events by System Organ Class and Preferred Term (Number of Participants and Occurrences)	FDAAA, EudraCT, by treatment, then summarized by pre-treatment, post-randomization, treatment emergent, and follow-up.	DR, SAC
2.13.	Safety	AE1	Summary of Adverse Events Leading to Permanent Discontinuation of Study Treatment or Withdrawal from Study by System Organ Class and Preferred Term	IDSL, by treatment	DR, SAC
Laboratory: Chemistry					
2.14.	Safety	PDT9	Summary of chemistry lab values	ICH E3 Includes: sodium, glucose, potassium, phosphate, calcium, ALT, AST, ALP, albumin, total protein, and total and indirect/direct bilirubin	DR, SAC
2.15.	Safety	LB1	Summary of change from baseline in chemistry lab values	ICH E3 Includes: sodium, glucose, potassium, phosphate, calcium, ALT, AST, ALP, albumin, total protein, and total and indirect/direct bilirubin	DR, SAC

## CONFIDENTIAL

205665

Safety: Tables					
No.	Population	IDSL / Example Shell	Title	Programming Notes	Deliverable
Laboratory: Hematology					
2.16.	Safety	PDT9	Summary of hematology lab values	
ICH E3 Includes: platelets, WBC count, basophils, eosinophils, lymphocytes, monocytes, neutrophils, haematocrit, RDW, CHr, HGB, Mean Hemocue HGB, MCHC, RBC, Reticulocyte, MCH, MCV, neutrophils segmented
 
Basophils/leukocytes (%), eosinophils/leukocytes (%), lymphocytes/leukocytes (%), monocytes/leukocytes (%), neutrophils/leukocytes (%), neutrophils segmented/leukocytes (%)
	DR, SAC
2.17.	Safety	LB1	Summary of change from baseline in hematology lab values	
ICH E3 Includes: platelets, WBC count, basophils, eosinophils, lymphocytes, monocytes, neutrophils, haematocrit, RDW, CHr, HGB, Mean Hemocue HGB, MCHC, RBC, Reticulocyte, MCH, MCV, neutrophils segmented
 
Basophils/leukocytes (%), eosinophils/leukocytes (%), lymphocytes/leukocytes (%), monocytes/leukocytes (%), neutrophils/leukocytes (%), neutrophils segmented/leukocytes (%)
	DR, SAC

## CONFIDENTIAL

205665

Safety: Tables					
No.	Population	IDSL / Example Shell	Title	Programming Notes	Deliverable
Laboratory: Other Screening Tests					
2.18.	Safety	PDT9	Summary of other screen test lab values	ICH E3 Includes: Serum hCG pregnancy test, Serum ferritin, Folate, Estradiol, Serum iron, Vitamin B12, FSH, Serum transferrin, UIBC, TSAT  Display only screening visits, query DM if other parameters are found at screening	DR, SAC
2.19.	Safety	PDT9	Summary of other screen test lab values, log transformed	ICH E3 Includes: Log transformed Serum ferritin and Serum iron  Display only screening visits	DR, SAC
ECG					
2.20.	Safety	EG2	Summary of ECG values	IDSL Includes: QTc, QTcB, QRS duration, and PR interval  ECG mean heart rate, QT interval, QTcF	DR, SAC
2.21.	Safety	EG2	Summary of change from baseline in ECG values	IDSL Includes: QTc, QTcB, QRS duration, and PR interval  ECG mean heart rate, QT interval, QTcF	DR, SAC

**CONFIDENTIAL**

205665

Safety: Tables					
No.	Population	IDSL / Example Shell	Title	Programming Notes	Deliverable
Vital Signs					
2.22.	Safety	PDT9	Summary of vital signs values	ICH E3 Includes: temperature, heart rate, SBP, and DBP	DR, SAC
2.23.	Safety	VS1	Summary of change from baseline in vital signs	ICH E3 Includes: temperature, heart rate, SBP, and DBP	DR, SAC
Additional Safety Tables					
2.24.	Safety	AE5A	Summary of Adverse Events by System Organ Class and Preferred Term and Maximum Intensity	ICH E3, by treatment, then summarized by pre-treatment, post-randomization, treatment emergent, and follow-up.	SAC
2.25.	Safety	LB17	Summary of Worst Case Chemistry Results by PCI Criteria Post-Baseline Relative to Baseline		SAC
2.26.	Safety	LB17	Summary of Worst Case Hematology Results by PCI Criteria Post-Baseline Relative to Baseline		SAC
2.27.	Safety	VS7	Summary of Worst Case Vital Signs Results by PCI Criteria Post-Baseline Relative to Baseline		SAC
2.28.	Safety	EG1	Summary of ECG Findings		SAC
2.29.	Safety	PAN1	Summary of COVID-19 Assessment		SAC

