5.1. Hemoglobin Stability Criteria

Entry into the study requires a stable Hgb between **8.5 and 11.5 g/dL, inclusive**. This is confirmed from **two** Hgb values obtained at the Screening Visit and Washout Visit, with both values between 8.5 and 11.5 g/dL. These will be taken via a validated point-of-care device to measure Hgb (i.e., HemoCue) prior to the dialysis session of the day. The value at the Washout Visit must not have decreased by more than 1.0 g/dL from the Screening Visit value. For subjects with a three-times weekly dialysis schedule, Hgb values must not be obtained on the first dialysis session of the week (e.g., if Monday-Wednesday-Friday schedule, the study visit cannot be on Monday). For subjects with a four- to five-times weekly dialysis schedule, Hgb values can be obtained on any hemodialysis session of the week.

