5.2. Inclusion Criteria

A subject will be eligible for inclusion in this study only if all of the following criteria apply:

AGE
1. ≥ 40 years of age, at the time of signing the informed consent.
TYPE OF SUBJECT AND DIAGNOSIS INCLUDING DISEASE SEVERITY
2. Hemoglobin: Stable Hgb 8.5 to 11.5 g/dL inclusive (See Section 5.1).
3. Dialysis frequency: On hemodialysis (HD, hemofiltration or hemodiafiltration) three- to five-times weekly for at least 4 weeks prior to screening.
4. Dialysis adequacy: A single pool $Kt/V_{urea} \geq 1.2$ based on a historical value obtained within the 3 months prior to screening in order to ensure the adequacy of dialysis. If Kt/V_{urea} is not available, then an average of the last 2 values of urea reduction ratio (URR) is at least 65%. NOTE: Only needs confirming at screening.
5. ESA treatment: Treated with an ESA (epoetins or their biosimilars, darbepoetin, or methoxy PEG-epoetin beta) for at least 4 weeks prior to screening.
6. Iron replacement therapy: Subjects may be on stable ($\leq 50\%$ change in overall dose and compliance of 80% of prescribed doses in the 4 weeks prior to and including the screening period) maintenance oral or IV (≤ 100 mg/week) iron supplementation. If subjects are on oral or IV iron, then doses must be stable for the 4 weeks prior to Washout.
7. Weight: Mid-week weight change between dialysis treatments $< 5\%$ as assessed post-dialysis at the Screening and Washout visits.
8. Antihypertensive Medication: Meets the following criteria: 
 • On at least 1 antihypertensive medication [excluding diuretics] 
AND
 
 • On that same medication and the same dose for at least 1 week prior to Washout

INFORMED CONSENT

9. Capable of giving signed informed consent as described in Section 10.2 which includes compliance with the requirements and restrictions listed in the consent form and in this protocol.
10. Willing and able to wear ABPM device for at least 25 hours on two separate sessions.

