6.4. Starting Dose and Dose Adjustment Algorithm

6.4.1. Subjects Randomized to Daprodustat

Subjects randomized to daprodustat will have doses adjusted, as required, to target Hgb within the range of 10.0-11.0 g/dL. Dose adjustments will be assigned **automatically** via the IVWRS based on the subject's Hgb value via onsite HemoCue assessment according to the following algorithms:

Day 1 (HemoCue Prior to Acute Challenge 1)

Hgb (g/dL)	Action or Dose
<7.5	Repeat HemoCue assessment on the same sample at same study visit to confirm; take average of 2 values. If confirmed, withdraw subject from the study.
≥7.5 and <10.0	6 mg daprodustat
≥10.0 and <11.5	4 mg daprodustat
≥11.5	Repeat HemoCue assessment on the same sample at same study visit to confirm; take average of 2 values. If confirmed, avoid dosing and continue washout for one additional week. If Hgb remains above 11.5 then withdraw subject from study.

The 8 week Hgb maintenance dosing will begin on Day 2, following Acute Challenge 1. Acute Challenge dosing is the same for all subjects on the daprodustat arm: 24 mg.

Days 15, 29, 43, & 57

The available dose steps for daprodustat are outlined below (highlighted boxes indicate starting doses). Dose adjustments will result in the daprodustat dose being increased or decreased by **one dose step**.

Hgb (g/dL)	Hgb change since previous study visit	Dose Adjustment
<7.5	Any change	Repeat HemoCue assessment on the same sample at same study visit to confirm; take average of 2 values. If confirmed, permanently discontinue study drug and withdraw subject from the study.
≥7.5 to <9.5	Decreasing or No change ¹	Increase to the next higher dose step
≥7.5 to <9.5	Increasing ²	Maintain dose

≥9.5 to ≤11.5	Any change	Maintain dose
>11.5 to <12.0	Increasing or No change	Decrease to the next lower dose step
	Decreasing	Maintain dose
≥12.0	Any change	Repeat HemoCue assessment on the same sample at same study visit to confirm; take average of 2 values. If confirmed, HOLD dosing for 2 weeks until next study visit. ³
≥7.5 to <12.0	increase of ≥1.3 in Hgb over 2 weeks ⁴	Repeat HemoCue assessment on the same sample at same study visit to confirm; take average of 2 values. If confirmed, decrease to next lower dose step,
≥7.5 to <12.0	Increase of > 2.0 in Hgb over previous 4 weeks (Days 29, 43, 57 ⁴ only)	Repeat HemoCue assessment on the same sample at same study visit to confirm; take average of 2 values. If confirmed, decrease to next lower dose step,

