7.5.1.1. ABPM Delay Due to High Hgb

Day 1: If the HemoCue Hgb is confirmed to be ≥ 11.5 g/dL, then avoid dosing and continue washout for one additional week. No other assessments should be performed for that subject during the visit. When the subject returns 7 days later, re-draw the Hgb for HemoCue and assess. If confirmed to be < 11.5 g/dL then progress with the remainder of assessments and perform Acute Challenge 1. If the Hgb remains high, the subject must be withdrawn.

Day 57: If the HemoCue Hgb is confirmed to be ≥ 11.5 g/dL, then hold the dose(s) of IP for 1 week. No other assessments should be performed for that subject during the visit. When the subject returns 7 days later, re-draw the Hgb for HemoCue and assess. If confirmed to be < 11.5 g/dL then progress with the remainder of assessments and perform Acute Challenge 2. If the Hgb remains high, the subject must be withdrawn.

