## CONFIDENTIAL

205665

Laboratory Parameters

 
Phosphate: Divide the mmol/L value by 0.323 to get the mg/dL value.
 
Lab values that are converted will be reported in place of original value
 

 
Heart rate and pulse rate can be used interchangeably
 
Total calcium and calcium can be used interchangeably
 
Total protein and protein can be used interchangeably
 
Total bilirubin and bilirubin can be used interchangeably
 
TSAT and transferrin saturation can be used interchangeably
 

 
Baseline HGB will be based either on the pre-dose value on Day 1 or screening value. Any unscheduled HGB values taken after the pre-dose value on Day 1 will not be used.
 

Normal Range Categories, PCI Criteria Categories and Worst Case Values

 
Normal range categories are: To Low, To Normal or No Change, To High
 
PCI criteria categories are: To Low, To w/in Range or No Change, To High
 
Subjects with a missing baseline value are to be assumed to have a normal/within range baseline value.
 
The determination of the worst-case post baseline value takes into account both planned and unscheduled assessments.
 
Worst case can be either High or Low. 
 
If a subject has both a decrease 'To Low' and an increase 'To High', then the subject is counted in both the 'To Low' and 'To High' categories.
 
If a subject was High at baseline and decreases to Low during the time interval, then the subject is counted in the 'To Low' category. Likewise, if a subject was low at baseline and increases to high during the time interval, then the subject is counted in the 'To High' category.
 
Subjects are only counted in the 'To Normal or No Change' or 'To w/in Range or No Change' category if their values are: 
 
When using normal ranges: Normal at baseline and have no high and no low values;
 
When using PCI ranges: Within range at baseline and have no high and no low values
 
High at baseline and do not change to low
 
Low at baseline and do not change to high
 
 
 
 
 

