**CONFIDENTIAL**

205665

ICH: Listings					
No.	Population	IDSL / Example Shell	Title	Programming Notes	Deliverable
21.	Safety	MH2	Listing of Medical Conditions for Participants with Liver Stopping Events	IDSL	DR, SAC
22.	Safety	SU2	Listing of Substance Use for Participants with Liver Stopping Events	IDSL	DR, SAC
All Laboratory					
23.	Safety	LB5	Listing of All Laboratory Data for Participants with Any Value of Potential Clinical Importance	ICH E3 Include abnormal ranges	DR, SAC
24.	Safety	LB5	Listing of Laboratory Values of Potential Clinical Importance	Include abnormal ranges	DR, SAC
25.	Safety	LB14	Listing of Laboratory Data with Character Results	ICH E3	DR, SAC
ECG					
26.	Safety	EG3	Listing of All ECG Values for Participants	IDSL	DR, SAC
27.	Safety	EG5	Listing of All ECG Findings for Participants with an Abnormal ECG Finding	IDSL	DR, SAC
28.	Safety	EG5	Listing of Abnormal ECG Findings	IDSL	DR, SAC
Vital Signs					
29.	Safety	VS4	Listing of All Vital Signs Data for Participants with Any Value of Potential Clinical Importance	IDSL	DR, SAC
30.	Safety	VS4	Listing of Vital Signs of Potential Clinical Importance	IDSL	DR, SAC

CONFIDENTIAL

205665

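### In SAP Table 2.26 a subject whose baseline hemoglobin is above 11 g/dL is reported as no change however far it rises, while small rises past 11 count as high; add baseline-independent counts (minor).

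*SAP*

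**What the plan says.** **The display.** Table 2.26, in the additional safety tables of SAP Section 14.12.5, is titled "Summary of Worst Case Hematology Results by PCI Criteria Post-Baseline Relative to Baseline". It uses the Safety population and has no programming note. Listing 24 in Section 14.12.11, "Listing of Laboratory Values of Potential Clinical Importance", uses the same limits, as does Listing 23.

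**The limits.** SAP Section 14.8.1 flags hemoglobin below 8.5 or above 11 g/dL. No reason is given for either figure.

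**The shift rule.** SAP Section 14.6.4: "PCI criteria categories are: To Low, To w/in Range or No Change, To High". The middle category takes subjects who are "High at baseline and do not change to low", and likewise those low at baseline who do not go high. A subject high at baseline who later goes low is counted as *To Low*. There is no category for moving further in the direction already flagged.

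**The protocol's ranges.**
- Section 5.1 requires two entry values, at Screening and Washout, "with both values between 8.5 and 11.5 g/dL".
- Section 7.5.1.1, for Day 1: "If the HemoCue Hgb is confirmed to be ≥ 11.5 g/dL, then avoid dosing and continue washout for one additional week". Dosing therefore goes ahead below 11.5.
- Section 6.4.1 adjusts daprodustat "to target Hgb within the range of 10.0-11.0 g/dL" and maintains the dose from 9.5 to 11.5 whatever the change. Section 6.4.2 gives epoetin alfa the same target, managed by local labelling.

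**The concern.** A worst-case shift table works when nearly everyone starts inside the limits. Here the high limit cuts through the range in which subjects may be dosed on Day 1. Two unlike things then happen in one table. Subjects who start just above 11 cannot register a rise of any size, and subjects who start just below 11 register a rise of a few tenths that leaves them in the daprodustat maintain-dose band.

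Excessive erythropoiesis is the first entry in the protocol's risk table (Section 12.3), which says experience is not yet enough to characterize that risk fully. Table 2.26 is the planned table most likely to be read as the count of hemoglobin excursions by arm. Apart from Table 1.10, which counts per-protocol exclusions including subjects who met any hemoglobin stopping criterion, no other planned table counts subjects by arm who crossed a stated hemoglobin level.

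**Working it through.** The plan states no figure to reproduce on this point. The check applies its rule to cases, then sizes the effect under assumptions.

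**1. Overlap of limit and permitted range.** Values above 11.0 and up to 11.5 are flagged high but lie inside both protocol ranges.
- Entry range 8.5 to 11.5: (11.5 − 11.0)/(11.5 − 8.5) = 0.5/3.0 = 17% of its width.
- Daprodustat maintain-dose band 9.5 to 11.5: 0.5/(11.5 − 9.5) = 0.5/2.0 = 25%.

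**2. The rule applied.** With low <8.5 and high >11:

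| Baseline | Worst post-baseline | Category in Table 2.26 |
|---|---|---|
| 10.6 | 11.1 | To High |
| 10.9 | 11.2 | To High |
| 11.3 | 13.2 | To w/in Range or No Change |
| 11.2 | 13.5 | To w/in Range or No Change |
| 11.2 | 8.0 | To Low |

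These results need no assumptions. For comparison, the daprodustat algorithm acts at 12.0 (Protocol 6.4.1), and SAP 14.6.4 uses 13 as one marker of excessive erythropoiesis.

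**3. How many subjects.** The documents give no hemoglobin mean or SD for this population, so everything here is assumed: baseline mean 9.8 to 10.5, SD 0.9, kept if at least 7.5 and below 11.5; three post-baseline values with mean 10.5 and SD 0.9; normal, with correlation 0.3 to 0.6 between a subject's values; dose reductions and holds ignored. Simulated shares, multiplied by the 62 subjects expected to be randomized:
- Above 11 at baseline: 6 to 18%, about 4 to 11 subjects (0.064 × 62 = 4.0; 0.181 × 62 = 11.2).
- Counted *To High*: 29 to 51%, about 18 to 32 subjects; 80 to 90% of these never reach 12.0.
- Reaching 12.0 or more: about 4 to 7 subjects. Of these, 14 to 51% are counted as no change, which is 1.0 to 2.0 subjects in both arms together.
- Reaching 13.0 or more and counted as no change: 0.07 to 0.13 of a subject.

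**4. Sensitivity.** With one common mean of 10.0 to 10.8, SD 0.7 to 1.0 and correlation 0.5, 34 to 57% of subjects reaching 12.0 started above 11 and so are not counted *To High*. At the extremes that is 0.004 × 0.41 × 62 = 0.1 subject (mean 10.0, SD 0.7) and 0.160 × 0.44 × 62 = 4.4 subjects (mean 10.8, SD 1.0).

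**The case against.** **The limit has a plausible basis.** Eleven is the top of the 10.0 to 11.0 target in both arms, so above 11 can be read as above target. This stands as a reason to keep the limit. The SAP does not state it, though, and the low limit of 8.5 matches the entry floor rather than the target floor of 10.0. The pair therefore follows neither range throughout.

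**Other outputs show hemoglobin.** This stands. Listings 23 and 24 would print the 13.2 because it exceeds 11; their fault is over-flagging. Tables 2.16 and 2.17 summarise values and changes for both central-laboratory and HemoCue hemoglobin. The 13 g/dL rule in Section 14.6.4 applies only around a thrombosis or ischemia event. A reader might infer that real excursions vanish from the safety reporting; the documents do not support that.

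**The low side.** A reader might infer an equal failure there, such as 8.2 falling to 7.2 shown as no change. The rule would do that, but an 8.2 baseline depends on which protocol text governs. The synopsis and Section 4.3 require 8.5 to 11.5 at Day 1 as well as at Screening, whereas Table 2 (Section 5.5.1.1) and Section 6.4.1 let dosing proceed from 7.5. A confirmed value below 7.5 also leads to withdrawal, so it would appear in disposition data.

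**The numbers are small.** This stands too. The percentages in step 3 sound large but amount to one or two people, and dose reductions and holds would lower the daprodustat count. The layout of the table's standard shell is also not in the documents and could add detail.

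**Conclusion.** The classification fault is real and follows from the text alone: in Table 2.26 a subject above 11 at baseline who does not later go low cannot be shown as rising, while small movements across 11 are counted as moves to high. Its reach is one safety shift table. The primary analysis, conduct and the underlying listings are unaffected.

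The size rests on assumed hemoglobin distributions: about 1 to 2 of 62 subjects reaching 12.0 and shown as no change, or 0.1 to 4.4 under the second set of assumptions. A reader might go further and infer that a difference between arms in excursions would be masked, or that the PCI limits must be replaced. Neither is shown. The counts are too small to establish masking, and the limit can be defended as the top of the target range. Severity: minor.

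**What to change.** In SAP Section 14.8.1, keep the hemoglobin limits and state their basis. In Table 2.26, add for each arm:
- the number and percentage of subjects whose worst post-baseline hemoglobin, regardless of baseline, is <7.5, ≥11.5, ≥12.0 and ≥13.0 g/dL. The first two levels are in the stopping table for both arms, 12.0 is in the daprodustat algorithm, and 13 is in SAP 14.6.4;
- a separate row for a further rise from a high baseline, and one for a further fall from a low baseline, taken out of the no-change category.

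Say whether each count uses central-laboratory or HemoCue values, since Day 1 dosing is decided on HemoCue and the hematology panel is central. These are reporting cut-points only and change no dosing or stopping rule.

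Separately, the protocol's Day 1 hemoglobin floor must be reconciled: 8.5 in the synopsis and Section 4.3, 7.5 in Table 2 and Section 6.4.1.

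The cost is a few table rows and a sentence or two of SAP text, with no new data; it should be settled before database release.
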